3.2 Primary endpoint/outcome

The primary quantitative outcome measures for this study will be work instability, as measured by the MS Work Instability scale, resilience, psychological flexibility, and self-efficacy. We want to check that the digital READY programme will continue to work as

intended when supported by trained healthcare professionals, therefore we would expect to see a psychological benefit for PwMS being supported to use the READY programme in an NHS setting.

We expect that this ACT-based programme should lead to increased resilience, psychological flexibility, and self-efficacy. We theorise that increasing these psychological factors should lead to a reduction in work instability. This should mean we see a significant reduction in work instability in participants who complete the digital READY for MS programme.

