Enrolment of NHS MS Centres **Refinement of Digital READY** Ethical Approvals & Digital READY is a web-based resilience training programme for Multiple Sclerosis Governance Enrolment of health professionals (HCPs) in MS (n=50) Digital introductory workshop delivered with Psychologist Outcome Measures: Pre-READY questionnaire (Baseline Psychological Flexibility; Qualitative feedback) HCPs complete Digital READY and training (n=50, 5 HCPs per site) 2a. Digital READY participation Week 3 interval support call (delivered by Psychologist) Development of troubleshooting toolkit Outcome Measures: Psychologist notes on troubleshooting, Post-intervention questionnaire pack (Psychological flexibility, User satisfaction) and 6m follow up questionnaire (Psychological flexibility) 2b. READY training workshop (delivered by Psychologist/Project manager) Outcome Measures: Knowledge/competencies test, qualitative feedback questionnaire Sub-set: Semi-structured audio-recorded research interviews post-READY **Enrolment of PwMS** (n=250; 5 per HCP, 25 per site) Screening: Employment status, MS-WIS (Work Instability), Consent to take part Outcome Measures: Pre-READY questionnaire (Baseline Psychological Flexibility, Work Instability, other psychological factors) **PwMS complete Digital READY** Digital READY participation Week 3 interval support call (delivered by HCP) Outcome Measures: HCP notes on troubleshooting, Post-intervention and 6m follow up questionnaire packs (Psychological flexibility, Work Instability, User satisfaction, other psychological factors) Sub-set: Semi-structured audio-recorded research interviews post-intervention and 6m Analysis and write up Primary outcomes: PWMS MS-WIS at 6m, PWMS Psychological flexibility at 6m, HCP Competency/Knowledge test

Secondary outcomes: HCP Psychological flexibility at 6M

Process evaluation: Qualitative interviews, notes and questionnaire responses

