6 PARTICIPANT ELIGIBILITY CRITERIA

6.1 Inclusion criteria

- Participants capable of giving informed consent
- Age 18 years or above
- Currently in paid employment with an intention to remain in employment for at least 6 months
- Phase 2: A registered healthcare professional or allied health professional who works in direct contact with patients diagnosed with Multiple Sclerosis OR
- Phase 3: An individual with a clinical diagnosis of Multiple Sclerosis and reporting a WI score ≥11/22 (on MS-WIS)

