7.1.1 Screening

Phase 2: HCPS

Healthcare professionals who wish to take part in the study must have responsibility for patients with Multiple Sclerosis as a part of their regular caseload.

Phase 3: PwMS

The MS Work Instability Scale (MS-WIS) will be used as a screening tool to identify subjects with medium or high levels of work instability (WI). In the baseline population from a longitudinal study of 208 PwMS, 20.2% had high WI, 37.0% had medium WI and 42.8% had low WI³⁸.

Potential participants for phase 2a (PwMS) who wish to be enrolled in the study will be invited to complete the MS-WIS. Respondents who report a score of ≥11 on the MS-WIS will be invited to enter the study.

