8.2 Statistical analysis plan

This is a hybrid trial assessing implementation and effectiveness of the digital READY programme in NHS settings.

In terms of effectiveness, this study seeks to understand who might benefit from the digital READY intervention and in what contexts. Participant outcomes (e.g. Work Instability, Psychological flexibility, Self-efficacy) will be measured at multiple time-points (baseline, week 8 and month 6). While the first step will be to assess for any change to outcome variables over time using repeated measures ANOVA, this provides only an overview of interventional impact and assumes homogenous change within the study group⁴². Latent Growth Curve Modelling (LGCM) can be useful to identify patterns within subgroups of a population to understand who benefits from an intervention and why⁴³. Latent Growth Curve Modelling (LGCM) will be used to determine trajectories over time. Changes from baseline to week 8 and baseline to month 6 will be assessed. Logistic regression models will be utilised to understand potential predictors of these trajectories. Specifically, the relationship between psychological flexibility, resilience, and work instability, how these change for participants from baseline to post-intervention and longer term, and if changes in these variables seem to be linked. If there is evidence of a relationship between work instability and resilience or psychological flexibility over time, such that increases in resilience or psychological flexibility relate to decreases in work instability, this would suggest that the READY programme could be effective in reducing work instability.

Lightning reports will be produced using rapid qualitative synthesis following a pre-defined framework³⁹. These lightning reports will enable iterative assessments of implementation that will inform the final qualitative assessments.

The process evaluation will help to identify contextual factors that may influence core processes of the intervention through qualitative inquiry.

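### PwMS are selected on a high MS-WIS and then tested, without a comparator, for a fall in MS-WIS; regression to the mean still running after T0 could produce that fall

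*Protocol*

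**What the plan says.** **Selection.** Protocol 7.1.1: "Respondents who report a score of ≥11 on the MS-WIS will be invited to enter the study". Section 6.1 repeats the threshold: "reporting a WI score ≥11/22 (on MS-WIS". Section 4 (Phase 3) adds that investigators and HCPs look for people who are having trouble at work. Section 7.1.1 gives the distribution of the scale in a cited cohort of 208: "20.2% had high WI, 37.0% had medium WI and 42.8% had low WI".

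**Outcome.** Section 3.2: "The primary quantitative outcome measures for this study will be work instability, as measured by the MS Work Instability scale", alongside resilience, psychological flexibility and self-efficacy. The trial flow chart fixes the time point: "Primary outcomes: PWMS MS-WIS at 6m". Section 3.2 then states the expected result: "This should mean we see a significant reduction in work instability in participants who complete the digital READY for MS programme".

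**Analysis.** Section 8.2: "the first step will be to assess for any change to outcome variables over time using repeated measures ANOVA". Latent growth curve models follow, and "Changes from baseline to week 8 and baseline to month 6 will be assessed". Section 8.2 also says that if flexibility or resilience rises as MS-WIS falls, this would point to READY possibly being effective.

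**Comparator.** There is none. Section 11.3 has all 250 PwMS invited to READY. Objective 2 (3.1) and section 4 nevertheless describe a test of effectiveness.

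**Timing.** MS-WIS is completed at T-1 and again in the T0 pack (sections 4 and 7.3, Table 3). The threshold is not re-applied at T0. The 24 hours shown under screening in Table 3 matches the time allowed to consider participation (7.1, 7.2); it does not separate T-1 from T0. No such interval is given.

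**The concern.** People chosen because a fluctuating score is high on one day tend to score lower later, treated or not. Here the selection scale is also an outcome scale, and picking people in current difficulty adds selection of the same kind. In a single group, a test of no change over time cannot separate that drift from a treatment effect.

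The repeat measurement at T0 is a genuine safeguard, but only against variation that has settled by then. If screening and baseline are completed within days of each other, a bad spell lasting weeks or months is present in both scores and resolves between T0 and month 6.

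Growth models do not escape this. Shared recovery from a bad spell would make flexibility rise as instability falls, which is the pattern that 8.2 reads as a favourable sign. At stake is the effectiveness conclusion under objective 2, and with it the decision about the large RCT that section 2 says this study precedes.

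**Working it through.** **The plan's own figure.** Section 8.1 needs 200 cases after 20% attrition: 200/(1 − 0.20) = 250, which reproduces. It rests on a rule of thumb for structural equation models, so there is no power figure for an MS-WIS change to check.

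**Inputs from the protocol.** Eligible share 20.2% + 37.0% = 57.2% (7.1.1); 200 completers (8.1).

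**Assumed, because the protocol gives none.** Normal scores with equal SD over time; two-sided alpha 0.05; r(T-1,T0) = 0.9; a range for the month-6 correlation, taken as the same for T-1 with month 6 and T0 with month 6.

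**Step 1: how far selection shifts the group.** The cut-off is c = Φ⁻¹(1 − 0.572) = −0.181. The mean of those selected is m = φ(c)/0.572 = 0.3924/0.572 = 0.686 SD above the cohort mean. Their variance at screening is v = 1 + c·m − m² = 0.405.

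**Step 2: expected fall from T0 with zero treatment effect.** Write a = r(T-1,T0) − r(T-1,month 6). The expected fall is a × 0.686 SD. The SD of the change is √[2 − 2·r(T0,month 6) − a²(1 − v)], and SE = SD/√200.

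**Step 3: chance of a significant result.** P = Φ(fall/SE − 1.96) + Φ(−fall/SE − 1.96).

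| Month-6 correlation | Fall (SD) | SD of change | SE | Fall/SE | P(p<0.05) |
|---|---|---|---|---|---|
| 0.90 (no decay) | 0 | 0.447 | 0.032 | 0 | 5% |
| 0.85 | 0.034 | 0.546 | 0.039 | 0.89 | 14% |
| 0.80 | 0.069 | 0.628 | 0.044 | 1.55 | 34% |
| 0.70 | 0.137 | 0.759 | 0.054 | 2.56 | 72% |
| 0.60 | 0.206 | 0.864 | 0.061 | 3.37 | 92% |

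A simulation of 3,000 trials per scenario, counting significant falls only, gave 33% at 0.80 and 71% at 0.70. With no decay (all correlations set to 0.8) it gave 2.6%: in that case about half of the nominal 5% lies in the favourable direction.

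**Step 4: sensitivity to the eligible share.** HCP pre-selection may make it higher than in the cited cohort. If 80% were eligible (assumed), m = 0.2800/0.80 = 0.350 SD, and steps 2 and 3 give 12%, 25% and 40% at month-6 correlations 0.8, 0.7 and 0.6. If 90% were eligible (assumed), m = 0.1755/0.90 = 0.195 SD, and the figures are 7%, 11% and 16%.

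**Step 5: why a simple correction fails.** It is natural to compute regression from the T-1/T0 correlation and subtract it from the T0-to-month-6 change. That regression took place before T0 and is not part of the later change. With all correlations 0.8, the true expected change from T0 is 0, yet the correction subtracts (1 − 0.8) × 0.686 = 0.137 SD. With SE = √0.4/√200 = 0.0447 the ratio is 3.07, a false deterioration in about 87% of trials.

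**The case against.** The strongest reply is that the plan already measures change from a second score. MS-WIS is repeated at T0, section 8.2 takes change from baseline, and section 9.1 lists the questionnaire times as baseline, week 8 and month 6. This stands, and it limits the point. A reader might infer that the selected group's whole fall from the screening score enters the analysis. On that reading, false significance would run from 60% (r = 0.9) to 99.6% (r = 0.6). The documents do not support it, because nothing in them plans to use the screening score as baseline.

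A reader might also infer that the null hypothesis is certainly false without treatment, or that the net bias is certainly favourable. Neither is established. If correlation with the screening score does not decay after T0, the error rate stays at 5%. The background describes a declining work course, and natural worsening would oppose regression.

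It is also fair that section 3.2 states an expectation and not a formal success criterion, that section 8.2 calls the ANOVA only an overview and says no more than that READY could be effective, and that section 2 places the study ahead of an RCT. These soften the claim but do not remove it: 3.2 ties the expected benefit to READY continuing to work as intended, and objective 2 is effectiveness.

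Finally, much of the detail could sit in an SAP that is not shown. That is true of the sensitivity analysis. It is not true of the wording in 3.2 and 8.2, nor of the screening-to-baseline interval and the retention of screening scores, which cannot be recovered after recruitment.

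**Conclusion.** The concern holds as a possibility that the design leaves open, not as a demonstrated bias. Selection on MS-WIS, a within-group test on MS-WIS and no comparator mean that a significant fall, or a fall linked to rising flexibility, is not evidence that READY is effective. The T0 measurement protects only against regression complete by T0, and no interval is set to make that likely.

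Under the protocol's 57.2% eligible share, false significance ranges from 5% to 92% over the correlations examined. The result depends almost wholly on how far correlation with the screening score decays by month 6, which the protocol does not inform. The figures also rest on normality, 200 completers and two-sided alpha 0.05, and they fall if the eligible share is higher. Severity: should-fix.

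**What to change.** 1. State in 8.2 that change in MS-WIS is measured from T0 and that the T-1 score serves eligibility only.
2. Set a minimum interval between T-1 and T0, and keep the T-1 scores of everyone screened, including those below 11.
3. Report the T-1 to T0 shift descriptively. Show the T0-to-month-6 change beside a range of expected untreated regression, computed over assumed T-1/T0 and T-1/month-6 correlations. Do not subtract regression computed from the T-1/T0 correlation.
4. Reword 3.2 and 8.2 so that an uncontrolled significant fall, or correlated change in flexibility and MS-WIS, is described as compatible with benefit and not as evidence of effectiveness.

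Separately, Table 3 marks MS-WIS only at screening and baseline, while the text of 7.4 collects it at week 8 and month 6. These need to be reconciled, since every change score depends on the later measurements.

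The cost is a short wait before baseline, retention of scores that are collected anyway, and a more modest headline. No extra assessments or participants are needed.

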3.3 Secondary endpoints/outcomes

Secondary outcomes will include psychological factors, such as anxiety and psychological impact of MS. Measuring these additional wellbeing factors will help us to determine how effective the digital READY programme could be for PwMS in other contexts.

3.4 Exploratory endpoints/outcomes

The key qualitative outcomes of this study will be to understand the contexts in which the digital READY programme can be supported by healthcare professionals to achieve these work-related and psychological outcomes. This will help to inform future adaptations to the READY for MS programme to additional contexts and settings.

4 TRIAL DESIGN

This study is a hybrid effectiveness-implementation trial, by which we are simultaneously trialling the effectiveness of an intervention but also exploring its implementation. We will focus on 'fidelity to function', meaning that the intervention still delivers the expected outcomes, while recognising that local adaptation is vital for any intervention to work because every setting and site is different.

We will use purposive sampling for this study, which means we will actively seek to include representatives of different demographic and socio-economic backgrounds.

The trial will include the following phases:

Phase 1: Programme refinement

Findings from the recent co-production and pilot study (MS PROACTIVE) will be utilised to refine and further develop the digital READY programme. The digital programme consists of an introductory module, 6 core modules on ACT factors (Mindfulness, Acceptance, Defusion, Observer Self, Values/Meaningful action, and Future Planning) then a final booster module to be completed after a 5-week break. Aside from the booster module, it is recommended to complete one module per week and each module takes around 40 minutes to complete. There are additional exercises that participants can complete under their own initiative between modules, with accompanying guided audio-recordings (e.g. Mindfulness of the breath). A workbook accompanies the digital content, with reflective written exercises for participants to complete during and between modules. This workbook forms a personal plan that participants can refer back to on completion of the programme.

Phase 2: Getting HCPs READY

MS healthcare professionals (HCPs) will be invited to a brief introductory (virtual) session to introduce the READY programme and meet the supporting psychologist. Following this virtual session, HCPs will be sent a digital baseline questionnaire that includes the CD-RISC-10 (Connor-Davidson Resilience Scale) and MPFI scales (Multidimensional PF Inventory) to measure baseline resilience and psychological flexibility, as well as free-text response questions to explore their expectations about the programme itself. HCPs will then be invited to complete the digital READY programme. The psychologist or researcher will conduct an interval support call with HCPs around their third week of doing the READY programme. The psychologist will keep notes on any troubleshooting that arises from these support calls, for example, any core concepts that the HCPs need further guidance with. Once HCPs complete the digital READY programme, they will be invited to complete a follow-up digital questionnaire pack including MPFI (post-intervention psychological flexibility) and SUS (user satisfaction) scales. After completing the READY programme and the follow up questionnaire, HCPs will be invited to take part in a digital training workshop delivered by the psychologist and myself. HCPs will complete a knowledge test following the workshop which will measure their ACT-based competencies. A digital free-text response questionnaire will also be sent to HCPs following the workshop to assess their experience of the training and any anticipated barriers to supporting others to complete the programme. HCPs will be invited to complete a further follow-up questionnaire at 6 months, including the MPFI scale to measure long-term impact of the READY programme. A sub-set of HCPs (purposively selected for diversity) will be invited to take part in semi-structured research interviews to understand their experiences of the programme, how they have understood the core concepts and their expectations around supporting PwMS to use the programme. We

will also seek to understand how, when, and in what contexts different HCPs might ask their patients about employment and difficulties at work. The week 3 support calls will be audio-recorded by the psychologist. Anonymised troubleshooting examples that arise from the Week 3 HCP-psychologist support calls will be utilised to develop 'case examples' in a 'troubleshooting toolkit'. This troubleshooting toolkit will be shared with PwMS who use the programme and a copy given to HCPs to aid support conversations.

Phase 3: PwMS

The CI and local PIs will work with HCPs to identify PwMS who are experiencing difficulties at work. The CI will also work to engage with different MS communities to invite PwMS to the study. PwMS will complete a screening MS-WIS (MS Work Instability Scale) and those with a score of 11 (medium WI) or above will be invited to enter the study. PwMS will complete a baseline digital questionnaire pack including MS-WIS, CD-RISC-10 (Connor-Davidson Resilience Scale), USE-MS (Unidimensional self-efficacy scale for MS) and MPFI (Psychological Flexibility) scales. Participants will be asked to consent to be contacted by a trained HCP who will offer support in completing the READY programme. PwMS will be provided with a link to the digital READY programme, the accompanying READY workbook and the troubleshooting toolkit. HCPs will conduct the interval support calls and record notes on any troubleshooting that arises from these support conversations. PwMS will be invited to complete a follow up digital questionnaire pack on completion of the READY programme, to measure post-intervention work instability, self-efficacy and psychological flexibility. PwMS will be invited to complete this questionnaire pack again at a further follow up time-point of 6 months. A small subset of PwMS will be invited to complete post-intervention and 6-month follow-up semi-structured interviews to explore their experience of the programme and any long-term impact.

This project will include a process evaluation, which is a method for collecting detailed information to understand if, how and in what contexts an intervention works. The process evaluation will consist of analysis from the HCP interviews, the PwMS interviews, qualitative feedback forms from HCPs and the notes from the HCP-PwMS interval support calls. Lightning reports will be utilised to provide iterative feedback on fidelity to function and identify any necessary adaptations to intervention delivery as the project progresses.

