Cardiff

[name]

Email: [contact]

[contact]

[name]

Managing Director and CEO of shift.ms

[name]

Email: [contact]

[contact]

ii. LIST of CONTENTS

GE	NERAL INFORMATION	Page No.
TIT	LE PAGE	1
RE	SEARCH REFERENCE NUMBERS	2
SIG	SNATURE PAGE	3
I. K	EY TRIAL CONTACTS	4
II. L	IST OF CONTENTS	6
III.	LIST OF ABBREVIATIONS	7
IV.	TRIAL SUMMARY	8
V. F	FUNDING AND SUPPORT IN KIND	9
VI.	TRIAL FLOW CHART	12
1	BACKGROUND	13
2	RATIONALE	15
3	OBJECTIVES AND OUTCOME MEASURES/ENDPOINTS	17
4	TRIAL DESIGN	18
5	TRIAL SETTING	21
6	PARTICIPANT ELIGIBILITY CRITERIA	21
7	TRIAL PROCEDURES	22
8	STATISTICS AND DATA ANALYSIS	31
9	DATA MANAGEMENT	32
10	MONITORING, AUDIT & INSPECTION	33
11	ETHICAL AND REGULATORY CONSIDERATIONS	34
12	DISSEMINIATION POLICY	38
13	REFERENCES	39

iii. LIST OF ABBREVIATIONS

Define all unusual or 'technical' terms related to the trial. Add or delete as appropriate to your trial. Maintain alphabetical order for ease of reference.

ACT Acceptance and Commitment Therapy

CI Chief Investigator

GCP Good Clinical Practice

GDPR General Data Protection Regulation

HCP Healthcare Professional ICF Informed Consent Form

IRAS Integrated research application system

ISF Investigator Site File
MS Multiple Sclerosis

MSIS-29 Multiple Sclerosis Impact Scale (29 items)
MS-WIS Multiple Sclerosis Work Instability Scale

MPFI Multidimensional Psychological Flexibility Index
NFI-MS Neurological Fatigue Index for Multiple Sclerosis

NHS National Health Services
PF Psychological Flexibility
PI Principal Investigator

PIS Participant Information Sheet
PPI Patient and Public Involvement
PwMS People with multiple sclerosis
READY(for MS) Resilience for Adults Everyday
REC Research and ethics committee
R&D Research and development

SE Self-efficacy

SUS System useability scale

TMF Trial Master File

TMG Trial Management Group
TSC Trial Steering Committee

USE-MS Uni-dimensional Self-efficacy Scale for Multiple Sclerosis

VAS Visual Analogue Scale

WI Work Instability

iv. TRIAL SUMMARY

Trial Title	Assessing NHS ImplemeNTation of an onlinE Resilience-training Acceptance and Commitment Therapy (ACT) programme to prevent job loss in MS			
Internal ref. no. (or short title)	INTERACT-MS			
Trial Design	Hybrid Feasibility-Implementation Trial			
Trial Participants	(1) MS Healthcare Professionals (2) People with Multiple Sclerosis (in employment)		
Planned Sample Size	(1) 50 (2) 250			
Treatment duration	12 weeks			

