7.4 Follow up data

Phase 2: HCPS

T1/Week 3: HCPs will be invited to complete the READY programme. The psychologist or CI will conduct an interval support call with HCPs between weeks 2-4 of completing the programme. The support calls will be audio-recorded. Anonymised troubleshooting examples that arise from these support calls will be utilised to develop 'case examples' in a 'Troubleshooting toolkit'. This troubleshooting toolkit will be shared with PwMS who use the programme and a copy given to HCPs to aid support conversations.

T2/Week 8: At week 8 from baseline (proposed completion of READY modules), HCPs will be invited to complete a follow-up digital questionnaire pack which will collect data on:

- Validated self-report scales for Resilience (CD-RISC-10), Psychological Flexibility (MFPI) and User Satisfaction (SUS; see Table 1).

After completing the READY programme and week 8 questionnaire, HCPs will be invited to take part in a digital training workshop delivered by the psychologist and CI.

HCPs will be invited to complete a knowledge test following the workshop which will measure their ACT-based competencies. A digital free-text response questionnaire will also be sent to HCPs following the workshop to assess their experience of the training and any anticipated barriers to supporting others to complete the programme.

T3/Month 6: HCPs will be invited to complete a further follow-up questionnaire at 6 months, which will collect data on:

- Validated self-report scales for Resilience (CD-RISC-10), Psychological Flexibility (MFPI) and User Satisfaction (SUS; see Table 1).

Table 2 - Schedule of procedures (Phase 2: HCPs)

Phase 2: HCPs	T-2 Approach	T-1 Screening (≥24h)	T0 Baseline (Pre- READY)	T1 Week 3 (± 7 days)	T2 Week 8 (Post- READY)	T3 Month 6
PIS given	Х					
Consent		Х				
Baseline Demographics - Date of birth - Sex - Gender identity - Ethnicity			Х			
Employment demographics - Professional group			Х			
Connor-Davidson Resilience Scale (CD-RISC-10)			Х		Х	Х
Multi-dimensional Psychological Flexibility Inventory (MFPI)			Х		×	Х
System Useability Scale (SUS)					Х	Х
Qualitative: Introductory workshop feedback form (Expectations about READY programme)			Х			
Qualitative: Interval support call audio- recording				Х		
Qualitative: Training workshop feedback form					Х	
ACT-based Competencies					Х	
Qualitative: Semi-structured interviews					Х	

Phase 3: PwMS

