T1/Week 3: The HCP will conduct an interval support call with HCPs between weeks 2-4 of completing the programme. HCPs will be encouraged to record notes from these support calls to contribute to lightning reports and the overarching process evaluation

T2/Week 8: Participants will be invited to complete follow-up questionnaire packs at week 8 from baseline. The questionnaire packs will be available to be completed digitally and will collect demographic information to include:

- Employment status
- Employment contract type
- Household income
- Number of sick days taken in last 6 months
- Relapse occurring in last 6 months
- Anchor VAS question on general health rating
- Validated self-report scales for Work Instability (MS-WIS), Resilience (CD-RISC-10), Psychological Flexibility (MFPI), Self-efficacy (USE-MS), Mood (HADS), and Impact of MS (MSIS-29) and User Satisfaction (SUS; see Table 1)

T3/Month 6: Participants will be invited to complete a further follow-up questionnaire pack at month 6 from baseline. The questionnaire packs will be available to be completed digitally and will collect demographic information to include:

- Employment status
- Employment contract type
- Household income
- Number of sick days taken in last 6 months
- Relapse occurring in last 6 months
- Anchor VAS question on general health rating
- Validated self-report scales for Work Instability (MS-WIS), Resilience (CD-RISC-10), Psychological Flexibility (MFPI), Self-efficacy (USE-MS), Mood (HADS), and Impact of MS (MSIS-29) and User Satisfaction (SUS; see Table 1)

.

Table 3 - Schedule of procedures (Phase 3: PwMS)

Phase 3: PwMS	T-2	T-1	T0	T1	T2	T3
	Approach	Screening	Baseline	Week 3	Week 8	Month 6
		(≥24h)	(Pre- READY)	(± 7 days)	(Post- READY)	
PIS given	Х					
Consent		Х				
Screening		Х				
Baseline Demographics - Date of birth - Sex - Confirmed MS diagnosis and subtype - Year of MS onset/ diagnosis - Gender identity - Ethnicity			Х			
MS History - MS subtype - Confirmed relapse(s) (last 6 months) - DMT status			X		Х	Х
 Employment demographics Employment status Employment contract type Household income Number of sick days (last 6 months) 			x			
General health VAS			Х		Х	Х
Multiple Sclerosis Work Instability Scale (MS-WIS)		Х	Х			
Connor-Davidson Resilience Scale (CD-RISC-10)			Х		Х	Х
Multi-dimensional Psychological Flexibility Inventory (MFPI)			Х		Х	Х
Unidimensional Self-efficacy scale for MS (USE-MS)			Х		Х	Х
Hospital Anxiety and Depression Scale (HADS)			X		X	Х

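### The T2 questionnaire has two incompatible triggers, finishing READY and week 8 from baseline, and week 8, headed Post-READY, falls about 4 weeks before the booster module

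*Protocol*

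**What the plan says.** On when T2 is sent, the protocol has two rules.

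- Section 4, Phase 3 (people with MS): "PwMS will be invited to complete a follow up digital questionnaire pack on completion of the READY programme". The stated purpose is to measure post-intervention outcomes, and no calendar week is given. Phase 2 of the same section uses the same trigger for healthcare professionals.
- Section 7.4, Phase 3: "Participants will be invited to complete follow-up questionnaire packs at week 8 from baseline". No completion condition is attached. For healthcare professionals it says: "At week 8 from baseline (proposed completion of READY modules), HCPs will be invited to complete a follow-up digital questionnaire pack".
- Tables 2 and 3 place T2 at week 8 and head the column Post-READY. Sections 8.2 and 9.1 also use baseline, week 8 and month 6.

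On what the programme contains, section 4, Phase 1 says "The digital programme consists of an introductory module, 6 core modules on ACT factors" and "then a final booster module to be completed after a 5-week break". On pace it says "Aside from the booster module, it is recommended to complete one module per week". The trial summary gives "Treatment duration 12 weeks".

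**The concern.** The two triggers select different people and measure them at different times. A completion trigger never reaches a participant who stops part-way, and for the others it makes the T2 date depend on how fast they work. Objectives 4 and 5 in section 3.1 concern how context shapes engagement and whether fidelity mediates outcome, so low engagers are the people whose T2 data matter most. Data not collected from them at T2 cannot be recovered at the analysis stage.

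A week 8 trigger avoids that loss but raises a second problem. The visit carries a label saying that the programme is over, whereas the protocol's own description has one module still to come. Section 8.2 assesses change from baseline to week 8 and also speaks of change to post-intervention. These are the same visit only if the booster is not part of the intervention, and the protocol nowhere says so.

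**Working it through.** **Step 1. The plan's own sample size.** Section 8.1 asks for at least 200 cases and assumes 20% attrition: 200 / (1 − 0.20) = 250. This reproduces the stated target exactly. The T2 problem does not change that figure.

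**Step 2. When the programme ends.** Inputs from section 4, Phase 1: 1 introductory module, 6 core modules, 1 booster, one module per week apart from the booster, and a 5-week break before the booster.

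- Modules in total: 1 + 6 + 1 = 8.
- Weekly modules: 1 + 6 = 7, ending at week 7.
- Booster: 7 + 5 = week 12, or up to week 13 if it is taken during the week after the break.
- If the introductory module is counted as week 0, the core modules end at week 6 and the booster falls at 6 + 5 = week 11, or up to week 12.

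The booster is therefore due at about week 12, range 11 to 13. The trial summary's 12-week treatment duration agrees, which suggests that the booster is counted as part of treatment.

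**Step 3. Where week 8 falls.**

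- Modules done at the recommended pace: 7 of 8.
- Gap to the booster: 12 − 8 = 4 weeks, with a range from 11 − 8 = 3 to 13 − 8 = 5.

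Week 8 matches the end of the weekly modules. It does not match the end of the programme as section 4 and the trial summary describe it.

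**Step 4. What the completion trigger would do.** The protocol gives no completion rate, so the rates here are assumptions. T2 invitations = 250 × completion rate.

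| Assumed completion | T2 invitations out of 250 |
|---|---|
| 90% | 225 |
| 80% | 200 |
| 70% | 175 |
| 60% | 150 |
| 50% | 125 |

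Below 80% completion, fewer than 200 people would have a T2 record even with no other loss. This applies only if section 4 is followed.

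**Step 5. Timing control.** Table 3 gives the week 3 contact a window of ± 7 days but gives T2 none. If a site worked from section 4, nothing in the schedule would limit how far T2 could move from week 8.

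**Step 6. Month 6.** Sections 4 and 7.4 agree on a 6-month follow-up, which falls well after weeks 11 to 13. The contradiction does not reach that visit.

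**The case against.** The strongest reply is that section 4 is a narrative overview and every operational passage gives a calendar time: section 7.4, Tables 2 and 3, section 8.2 and section 9.1 all say week 8. The parenthesis in the section 7.4 text for healthcare professionals equates week 8 with finishing the modules, so completion in section 4 may be shorthand for the scheduled end of the weekly ones. Measuring then, ahead of a booster, is a legitimate design choice.

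Much of this stands. Week 8 is the likelier rule in practice, which makes a mislabelled visit the likelier harm and loss of non-completers the conditional one. The shorthand reading is not secured, however. The parenthesis appears only in the part on healthcare professionals, and no passage excludes the booster from completion.

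A reader might infer several stronger points that the documents do not support:

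- **That the primary result is compromised.** The flow chart places work instability and psychological flexibility in people with MS at 6 months, after the booster is due. Usability (SUS) is also repeated at month 6.
- **That only completers will be analysed.** Section 3.2 does expect a "significant reduction in work instability in participants who complete the digital READY for MS programme", but this is an expectation drawn from theory and defines no analysis set. The same section also expects benefit in people supported to use READY, without that restriction.
- **That the treatment effect is overstated by a calculable percentage.** That would need a completion rate, an assumption about change in non-completers and a completer-only analysis. The protocol supplies none of these.
- **That the growth model is misspecified.** Section 8.2 names the model but does not say how time is coded, a detail that may be left to the SAP.

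**Conclusion.** The point holds as a contradiction in the visit schedule together with a wrong label. The protocol states two triggers for T2 that cannot both be followed. One would leave non-finishers uninvited and let timing vary. The other heads as Post-READY a visit that comes after 7 of 8 modules and about 4 weeks (3 to 5) before the booster of a programme stated to last 12 weeks.

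The effect is confined to the baseline-to-week-8 contrast and the middle point of a three-point growth curve. The timeline assumes the recommended pace of one module per week. The T2 counts in the working rest on assumed completion rates and apply only under the completion trigger. The contradiction itself needs no assumption. It should be corrected because the completion rule, as written, permits an exclusion at T2 that later analysis cannot undo.

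**What to change.** Reconcile the passages and leave the READY programme as it is.

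1. In section 4, Phases 2 and 3, replace the completion trigger for the follow-up pack with the trigger already in section 7.4, week 8 from baseline. State that the pack goes to every enrolled participant whatever they have completed.
2. In Tables 2 and 3, relabel T2 as after the weekly modules and before the booster. Use the same description in section 8.2, so that the baseline-to-week-8 change is not reported as change after the whole programme.

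The cost is an edit to the wording and a fixed-date setting in the questionnaire platform. Sections 7.4 and 9.1 already collect at week 8, so no visit or questionnaire is added.
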